RO7121661 will be administered IV with a flat dose. The starting dose will be 70 mg and the maximum dose explored will be 2.1 g. Since RO7121661 will be administered Q2W in Part A, the cycle length will be defined as 14 days.

This part of the study will enroll participants with solid tumors who have progressed on a cancer therapy or who are not amenable to standard of care. At least DLT evaluable participants will be enrolled in each cohort during the dose escalation. Dose escalation will be carried out according to a modified continual reassessment method (mCRM) with escalation with overdose control (EWOC) design, with the aim of identifying the MTD/RDE of RO7121661.

The maximum total number of participants in the dose escalation portions of Part A will be approximately DLT evaluable participants. A dose cohort can be extended to enroll additional participants, potentially enriched in certain tumor types and/or characteristics (approximately) to confirm safety, PK and/or RO data.

Part B

Part B1 and/or B2 and/or B4 and/or B5 may commence upon completion of Part A. The starting dose of RO7121661 for Part B is 2.1 g as derived from the RDE in Part A determined by safety, PK and/or RO and/or the biomarker profile. Part B3 will not proceed prior to generation of data from the initial CPI experienced indication(s).

Patients enrolled in Part B expansions have more specific limitations of prior therapies for inclusion than during the dose escalation. Patients enrolled in Part B1 (CPI experienced melanoma) must have had treatment with approved anti-PD-L1/anti-PD-1 checkpoint inhibitors. Patients enrolled in Part B2 (CPI and platinum experienced, PD-L1 expression ≥ 1% NSCLC) must have had a checkpoint inhibitor and platinum chemotherapy. Patients enrolled in Part B3 (untreated, CIT naïve NSCLC with PD-L1 expression ≥ 50%) should not have had any prior therapy. Patients enrolled in Part B4 (CPI naïve SCLC) and B5 (CPI-naïve ESCC) should not have had any prior checkpoint inhibitor therapy but may have had chemotherapy. Specific details for Part B Expansions are included in the Inclusion and Exclusion Criteria.

In Part B (tumor specific expansion cohorts) approximately participants will be included per indication. Part B cohorts may run in parallel staggered or sequentially.

Parts A and B

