Pembrolizumab has also received approval for treatment-naïve patients with advanced NSCLC without driver mutations and with tumor proportion score (TPS) ≥50% or high tumor PD-L1 expression, based on the KEYNOTE-024 Phase III study (Reck et al 2016). Pembrolizumab also received accelerated approval in combination with platinum and pemetrexed in first line treatment-naïve non-squamous patients irrespective of PD-L1 status based on Phase II results in KEYNOTE-021 (Langer et al 2016) and confirmed in the Phase III KEYNOTE-189 study (Gandhi et al 2018). Recent results from CheckMate 227, a Phase III trial in patients with chemotherapy-naïve stage IV or recurrent NSCLC demonstrates improvement in PFS with first-line nivolumab plus ipilimumab than with chemotherapy among patients with a high tumor mutational burden (TMB), irrespective of PD-L1 expression level. (Hellmann et al 2018) supporting a potential role for the use of TMB as a selection marker for treatment. Furthermore, durvalumab was approved for patients with unresectable Stage III NSCLC based on Phase III results in the PACIFIC study (Antonia et al 2017).

2.2.2 Small Cell Lung Cancer Patients: Checkpoint Inhibitor Naïve

In 2012, the World Health Organization (WHO) estimated the worldwide incidence of new lung cancer cases was 1.8 million, resulting in approximately 1.6 million deaths and accounting for about 13% of total cancer diagnoses (Ferlay et al 2012). In the Western World, approximately 13% of the lung cancers that are diagnosed are small cell lung cancer (SCLC). SCLC occurs primarily in patients with a history of tobacco use and originates from neuroendocrine cell precursors. It is characterized by rapid growth, high response rates to both chemotherapy and radiotherapy, and the development of treatment resistance in patients with metastatic disease (Früh et al 2013).

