data from PD-1 inhibitors demonstrate benefit in the ESCC population (see Section 2.2.4). Compared to esophageal adenocarcinoma PD-L1 expression is enriched in ESCC, which might increase tumor susceptibility in these patients to elimination following immune checkpoint inhibition. The reported prevalence of PD-L1 expression in ESCC ranges from 15% to 83% in tumor cells, and from 13% to 31% in tumor-infiltrated immune cells (Jiang et al 2017, Lam et al 2017, Guo et al 2018, Qu et al 2016). TIM-3 has also been shown to be expressed on TILs in patients with ESCC (Zhao et al. 2020). RO7247669 may therefore have the potential to be a therapeutic option for patients with ESCC.

For CIT naïve previously untreated NSCLC patients, focus will be on those participants with at least≥50% PD-L1 expression as based on pembrolizumab study KEYNOTE-024 (Reck et al 2016), as these are participants felt to have the highest opportunity for response to PD-1 therapy and therefore may gain additive activity from the TIM-3 mechanism of the BsAb.

Other indications may be explored in the tumor-specific expansion cohorts in Part B based on emerging clinical data from the Part A dose-escalation and/or based on emerging scientific rationale. These additional indications may be proposed and added to this study for Part B via an amendment.

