 - Adjuvant chemo-radiation treatment with anti-PD-1/PD-L1 inhibitors or consolidation treatment with anti-PD-1/PD-L1 inhibitors after definitive chemo-radiation therapy is allowed but participants do require an additional line of anti-PD-1/PD-L1 treatment in the metastatic setting.

Specific Inclusion Criteria for Part B3 Expansion in PD L1 High, CPI Naïve, First **Line NSCLC Cohort**

28. Participants with histologically confirmed advanced NSCLC with PD-L1 high defined as ≥ 50% PD-L1 expression based on immunohistochemistry using antibody clone 22c3, sp263, or 28-8. Expression will be determined in a fresh tumor biopsy collected during study screening or a possibly available archival sample, provided that the latter is not older than 12 months and has been obtained after failure of last CPI treatment line and prior to receiving study treatment.

Specific Inclusion Criteria for Part B4 Expansion in CPI-Naïve SCLC Cohort

- 29. Participants must have histologically confirmed SCLC.
- 30. Participants may have had prior chemotherapy, radiation therapy or declined approved therapies for SCLC.

Additional Specific Inclusion Criteria for Part B5: CPI Naïve Esophageal **Squamous Cell Carcinoma**

- 31. Participants whose major lesion was histologically confirmed squamous cell carcinoma or adenosquamous cell carcinoma of the esophagus.
- 32. Patients who have previously received not more than 1 prior lines of treatment for metastatic disease prior to enrolling to the study. The prior line must be a fluoropyrimidine and platinum-based regimen and patients must have experienced progressive disease.
- 33. Patients who underwent a radical resection (R0 resection confirmed) in conjunction with chemotherapy with fluoropyrimidine and platinum-based drugs including neoadjuvant/adjuvant therapy and chemo-radiation (including patients who underwent chemo-radiation followed by salvage surgery) are allowed.
 - If recurrence was confirmed by imaging within 24 weeks after the last dose of the treatment, the therapy should be counted as equivalent to metastatic treatment. Such patients are eligible and do not require an additional line of therapy in the metastatic setting.

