
Specific Exclusion Criteria for Part B3 Expansion (1st line CIT naïve patients)

- 29. Prior therapy for metastatic disease is not permitted i.e., treatment with any immune CPIs (such as anti-PD-L1/PD-1, CTLA-4), immunomodulatory mAbs, other immunomodulator therapies, chemotherapy or TKIs.
- 30. Adjuvant anti-PD-1 or anti-PD-L1 therapy is not allowed. Adjuvant chemotherapy is permitted as long as treatment was administered > 6 months prior to Cycle 1, Day 1.

Specific Exclusion Criteria for NSCLC patients (Part B2)

31. NSCLC patients with the following mutations, rearrangements, translocations are not eligible for Part B2: EGFR; ALK; ROS1, BRAFV600E, NTRK

Specific Exclusion Criteria for Part B4 Expansion (CPI-naïve SCLC patients)

32. Prior therapy with any immune CPIs (such as anti-PD-L1/PD-1, anti-CTLA-4), is not permitted.

Specific Exclusion Criteria for Part B5: CPI Naïve Esophageal Squamous Cell Carcinoma

33. Prior therapy with any immunomodulatory agents including CPIs (such as anti-PD-L1/PD-1, anti-CTLA-4), is not permitted.

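### The driver-alteration exclusion (criterion 31) covers Part B2 only, so Part B3 as written can enroll patients outside the population that its rationale cites

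*Combined protocol and SAP*

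**What the plan says.** Criterion 31 is the only eligibility rule on driver alterations in NSCLC. In Section 5.2 and in Synopsis 1.1 it reads "NSCLC patients with the following mutations, rearrangements, translocations are not eligible for Part B2: EGFR; ALK; ROS1, BRAFV600E, NTRK". Its heading is also limited to Part B2.

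Part B3 has its own criteria:
- Inclusion 28 asks for "Participants with histologically confirmed advanced NSCLC with PD-L1 high defined as ≥ 50% PD-L1 expression" and sets no molecular condition.
- Exclusion 29 bars earlier treatment for metastatic disease, ending its list with "other immunomodulator therapies, chemotherapy or TKIs".
- Exclusion 30 bars adjuvant anti-PD-1/PD-L1 therapy and limits adjuvant chemotherapy by timing.
- The design summary in Synopsis 1.1 adds: "Patients enrolled in Part B3 (untreated, CIT naïve NSCLC with PD-L1 expression ≥ 50%) should not have had any prior therapy".

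On the rationale, Section 4.3.1 explains the B3 focus by "PD-L1 expression as based on pembrolizumab study KEYNOTE-024". Section 2.2.1 describes the approval resting on that study as being for "treatment-naïve patients with advanced NSCLC without driver mutations" and a tumor proportion score of at least 50%. Section 2.3 gives the B3 question: whether targeting TIM-3 adds activity over what PD-1 targeting alone would be expected to give.

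**The concern.** Two NSCLC cohorts test the same PD-1/TIM-3 agent, but only one screens out tumors with a driver alteration, and no reason is given for the difference. An untreated patient with, say, an ALK rearrangement and PD-L1 expression of 60% does not fail any B3 criterion on molecular grounds.

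This matters because B3 has no control arm. Its primary endpoints (ORR, DCR, DoR, PFS) gain meaning only against what is expected in comparable patients, and the protocol itself points to the comparable patients it has in mind. If the enrolled cohort is wider than that population, a reader cannot tell how much of a difference from expectation comes from the patient mix.

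**Working it through.** **Step 1. Does any other rule close the gap?** I checked each text that governs entry to B3.

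| Text | Bears on driver status in B3? |
|---|---|
| General inclusion 1-2 and 4-16, biopsy criterion 17 | No |
| Inclusion 3 (progression, no effective standard therapy, or declined therapy) | Part A only |
| Inclusion 28 (B3) | Histology and PD-L1 only |
| General exclusions 1-25 | No driver alteration named |
| Exclusions 29-30 (B3) | Bar earlier treatment, not the alteration |
| Exclusion 31 | Part B2 only |
| Schedule of activities (Section 1.3) | No EGFR, ALK, ROS1, BRAF or NTRK eligibility test listed |
| Section 4.1.5 (sponsor approval of pre-screened participants) | No molecular rule stated |

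General exclusion 14 is a catch-all for other conditions that may affect interpretation. It cannot sensibly be read to cover driver status: if it did, criterion 31 would be unnecessary for B2.

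**Step 2. Which patients are admitted?** Exclusion 29 concerns treatment for metastatic disease, and exclusion 30 does not mention adjuvant TKIs. The admitted driver-altered patients are therefore those with no TKI for metastatic disease.

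**Step 3. Does this match the cited basis?** Section 4.3.1 takes the B3 focus from the first-line pembrolizumab study; Section 2.2.1 describes the population supported by that study as without driver mutations; Section 2.3 asks about activity over PD-1 targeting alone. Read together, they define a reference population that the B3 criteria do not enforce.

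**Step 4. How large could the effect be?** The plan states no figure to reproduce. The B3 sample size is redacted, and the documents give no driver share and no response rate by driver status. What follows is illustration only; every input is assumed.

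Shift in cohort ORR = f × g, where f is the driver-altered share and g is the ORR gap.
- f = 5%, g = 10 points: 0.05 × 10 = 0.5 points.
- f = 10%, g = 20 points: 0.10 × 20 = 2 points.
- f = 20%, g = 40 points: 0.20 × 40 = 8 points.

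**Step 5. Would the zero-response rule in Section 9.5 be affected?** P(no response) = (1 − p)^n. The interim n is redacted; assume n = 10 and an ORR of 30% without alterations.
- No altered patients: 0.70^10 = 2.8%.
- f = 10%, g = 20 points, so p = 28%: 0.72^10 = 3.7%.
- f = 20%, g = 30 points, so p = 24%: 0.76^10 = 6.4%.

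At n = 20 the same three cases give 0.08%, 0.14% and 0.41%. In absolute terms the rule changes little.

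**The case against.** The strongest reply is that several more serious conclusions do not follow. Most of that reply stands.

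- A reader might infer that the protocol names a driver-negative benchmark for B3. It does not. The link joins Section 4.3.1 to a background sentence in Section 2.2.1, and no reference ORR is given. It is a cited basis, not a stated benchmark.
- A reader might infer that the gap is what prevents attribution of an effect to TIM-3. Attribution is limited in any case: the study is non-randomized, has no PD-1-only arm, states no hypotheses and plans descriptive analysis. Extending criterion 31 would not change that.
- A reader might infer a known bias in ORR. Neither the size nor the direction is in the documents; Section 2.2.1 reports where these agents are commonly used, not how altered tumors respond. The shift may also be small next to sampling error. If all of the roughly 280 planned participants were split equally over five Part B cohorts, each would have 280/5 = 56. At an assumed ORR of 45%, the 90% interval half-width is 1.645 × √(0.45 × 0.55/56), or about 11 points, which exceeds the largest illustrated shift. Sampling error, however, does not remove a mismatch in who is enrolled.
- A reader might take Section 9.5 as a commitment to compare with standard of care. It says only that predictive probabilities might be used, and the futility analyses are non-binding.

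There are also partial safeguards. The sponsor approves pre-screened participants, and B3 opens only after data from the checkpoint-inhibitor-experienced cohorts. The first states no molecular rule. The second delays the problem, which leaves time to correct it.

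None of this supplies a rule that excludes these patients or a reason for treating B2 and B3 differently.

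**Conclusion.** The point holds as a mismatch between the B3 eligibility criteria and the B3 rationale. Followed as written, the plan allows driver-altered patients with high PD-L1 expression and no TKI for metastatic disease into a cohort whose cited basis is a population without driver mutations. The consequence is for interpretation of B3's primary efficacy results and of any comparison with expected standard-of-care activity.

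The textual finding needs no assumption. The 0.5 to 8 point range for ORR rests wholly on assumed shares and gaps and should not be quoted as an estimate. The documents do not support a claim that B3 would be biased by a known amount or that the futility rule would be impaired.

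**What to change.** Before B3 opens, reconcile criterion 31 with the B3 rationale in Sections 5.2 and 1.1. Either of two routes would do:

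1. Extend the heading and the text of criterion 31 to Parts B2 and B3. This is the simplest change.
2. Keep the present scope, state why B3 differs from B2, and report B3 efficacy separately by driver status.

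Under either route, state which molecular documentation is acceptable for both cohorts. The protocol names no source of molecular results for B2 now, so there is no existing rule to carry over.

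The first route costs a short amendment in two places, the loss of a minority of B3 candidates and a molecular result on file for each participant. The second loses no candidates but also needs the molecular result, and its subgroups may be too small for more than listing.

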5.3 LIFESTYLE CONSIDERATIONS

Participants will be expected to follow protocol requirements for contraception (see) and study center rules during visits, but there are no other lifestyle restrictions during the study. There are no study-specific restrictions to meals and dietary requirements.

5.4 SCREEN FAILURES

Screen failures are defined as participants who consent to participate in the clinical study but are not subsequently entered in the study.

All screening evaluations must be completed and reviewed to confirm that participants meet all eligibility criteria before entering the study. The Investigator will maintain a screening log to record details of all participants screened and to confirm eligibility or record reasons for screening failure. Individuals who do not meet the criteria for participation in this study (screen failure) may be re-screened, *after advice from the Sponsor*. In case of uncertain or questionable results, any of the tests performed during Screening may be repeated before study drug administration to confirm eligibility (or clinical significance).

Biopsy samples will only be entered in the eCRF and analyzed for enrolled participants.

In the event that a fresh biopsy is taken during the screening period and the participant is not enrolled into the study, the formaldehyde-fixed paraffin-embedded (FFPE) biopsy block can be returned to the site upon site request.

5.5 RECRUITMENT PROCEDURES

Participants will be identified for potential recruitment using pre-screening enrollment logs, Institutional Review Board (IRB)/Ethics Committee (EC) approved newspaper/radio advertisements, and mailings prior to consenting to take place on this study.

6. TREATMENTS

Study treatment is defined as any investigational treatment(s), marketed product(s), placebo, or medical device(s) intended to be administered to a study participant according to the study protocol.

All investigational medicinal products (IMPs) required for completion of this study (RO7121661) will be provided by the Sponsor. All study drug administration will be at the study center under supervision of site staff.

6.1 TREATMENTS ADMINISTERED

Table 5 summarizes the treatments administered.

Table 5 Summary of Treatments Administered

	Ro 712-1661/F01-01 (Active)	Ro 712-1661/F02-01 (Diluent)	
Administration	Intravenous ^a		
Dosage form	Concentrate for solution for i.v. infusion	Solution for infusion. For i.v. infusion	
Concentration of RO7121661	50 mg/mL	0 mg/mL	
Primary packaging	6-mL colorless glass vial	20-mL colorless glass vial	
Extractable volume	6.0 mL	20.0 mL	

^a 0.2- μm inline filter to be used for drug administration.

Guidelines for dosage modification and treatment interruption or discontinuation are provided in Section 6.6 or Section 7, respectively.

Please see the Investigator's Brochure and Pharmacy Manuals for more details.

6.1.1 RO7121661

Ro 712-1661/F01-01 drug product can be administered IV, either undiluted or diluted, as directed in the study protocol and the Pharmacy Manual. If diluted, Ro 712-1661/F01-01 drug product must be diluted either in 0.9% (w/v) sodium chloride solution or in the Sponsor's diluent, Ro 712-1661/F02-01, as directed in the Pharmacy Manual. A 0.2 μ m inline filter must be mandatorily used with the infusion set during administration.

In Part A, the initial dose and subsequent infusions of RO7121661 will be delivered over 120 ± 10 minutes (although the infusion may be slowed or interrupted for participants

who experience infusion-associated symptoms; see Section 8.3.8.1), followed by a 90-minute observation period. If no IRR has been reported, the catheter may be removed at the end of the observation period.

In Part B, the initial dose of RO7121661 will be delivered over 120 ± 10 minutes (although the infusion may be slowed or interrupted for participants who experience infusion-associated symptoms; see Section 8.3.8.1), followed by a 90-minute observation period. If the 120-minute infusion is tolerated without infusion-associated AEs, the second infusion may be delivered over 60 ± 10 minutes, followed by a 60 minute observation period. If the 60-minute infusion is well-tolerated, all subsequent infusions may be delivered over 30 ± 10 minutes, followed by a 30-minute observation period. If no IRR has been reported, the catheter may be removed at the end of the observation period.

During infusion, vital signs (including, if possible, supine diastolic and systolic blood pressure, pulse rate, and temperature) must be monitored as described in the SoA (Section 1.3). Vital signs during the infusion are not required to be captured in the eCRF, unless abnormalities are observed.

If feasible, the line for drawing blood for PK samples (opposite extremity to the one with the infusion line) will remain in place until the 24-hour sample is taken.

Dose, date, and time of the infusion start, date and time of end of infusion, total dose administered, interruption or adjustment of infusion rate, and reason will be recorded for each participant. If the infusion is interrupted, the date and time of stopping and resuming will be recorded.

6.1.2 Pre-medication

No pre-medication is foreseen prior to the first administration of RO7121661.

However, if administered, all pre-medications should be captured as concomitant medications in the participant's electronic Case Report Form (eCRF).

If Grade ≥ 2 IRRs or tumor inflammatory events occur in the majority of participants during dose escalation, the utility of prophylactic pre-medications including paracetamol and antihistamine may be considered for newly enrolled participants and premedication regimen and schedule should be *discussed* between Sponsor and Investigator(s).

Participants who experienced a Grade 2 or higher IRR on a previous infusion should be pre-medicated for subsequent infusions. Premedication regimens for subsequent cycles may be reduced or omitted in case of \leq Grade 1 events in the previous cycle.

 Paracetamol (500-1000 mg oral [PO] or IV) and diphenhydramine (25-50 mg PO or IV; or an alternative histamine H1/2 antagonist at an adequate dose). If a participant experienced a Grade 3 IRR, the same will apply in addition to corticosteroid 200 mg hydrocortisone IV (or equivalent dose of another corticosteroid).

For participants who experience an IRR-like reaction with a single and isolated symptom, such as fever that occurs within 24 hours after the study treatment infusion was completed, the use of pre-medication such as paracetamol, anti-histamine, and corticosteroids is not foreseen prior to subsequent RO7121661 administrations. The event will be reported as a single AE (e.g., fever). Pre-medication with corticosteroids for those participants at subsequent infusions needs approval from the Sponsor and the treatment and management at the time of a single and isolated event is at the discretion of the Investigator.

All pre-medications should be captured as concomitant medications in the participant's electronic Case Report Form (eCRF).

